## **Objectives**

### **Primary Objectives**

The primary objective of the Iron Supplementation Trial is to determine the potential for an iron supplementation strategy to increase blood donations in Ghana. To determine this potential, the study will investigate the feasibility and acceptability of this intervention along with key return blood donation measures among first-time blood donors found to have low haemoglobin or found to have IDA or be ID within the catchment areas of the SZBC. These aspects of the potential for this intervention will be

operationalized as follows:

- **Feasibility** of recruitment, enrolment, retention, and adherence will be evaluated with a target retention rate > 90% of all participants recruited completing the trial. If we are unable to achieve this target, alternative strategies will be considered for the UH3 phase.
- **Acceptability** will involve establishing the safety profile of 3 times weekly low dose ferrous sulphate (65mg elemental iron) supplements among those assigned to iron supplementation at enrolment. This safety profile will be established by comparison to a similar group of participants who do not receive iron supplementation. Participant and key informant views and perspectives of barriers and recommendations for using iron supplementation and nutritional counselling to increase the blood donor pool will also be investigated with participant questionnaires. In addition, FGDs and key informant interviews will provide critical insights into the acceptability of this intervention.
- **Key blood donation measures** include haemoglobin levels at 4 months, the change in haemoglobin concentration, ferritin levels at 4 months, the proportion of participants with corrected ID, the proportion of participants who return to the blood centre to donate blood and the proportion of returners who are able to successfully donate (not deferred). In addition, the incidence of ID and IDA among blood donors will be determined among those who consent to the Iron Supplementation Trial at screening.

To achieve this objective, a pilot parallel groups trial will be conducted for one year. This allows for enrolment over a maximum of 6 months and 6 months of follow-up for the last individual enrolled. The follow-up period incorporates 4 months of the iron supplementation intervention.

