## 4 Administration of Study Treatment

Potential first-time donors will be asked if they are interested in participating in a study of the prevalence of ID and IDA and the impact of iron supplementation on haemoglobin levels and repeat donation. Those who express interest, consent to the study, and are eligible will be asked to return within 3 weeks. During this 3-week period a FBC, a peripheral blood film analysis, and a plasma ferritin measurement will be conducted, and participants will be classified as iron supplement participants (e.g., anaemic, ID, IDA) or otherwise (which we refer to as controls in this protocol).

Those found to be anaemic, ID or IDA will receive oral iron supplementation and nutritional counselling. The oral iron supplements will be ferrous sulphate 200mg (65mg Elemental iron). The iron supplements are already available at the Korle-Bu Teaching Hospital Pharmacy. The study principal investigators and study pharmacist will ensure the medicine is stored properly and dispensed only when needed for study participants. The following will be monitored and completed on a periodic basis to ensure the medicine is within study guidelines, pharmaceutical compliance, and manufacturer guidelines:

Drug Accountability Record.

Iron supplement Safety and Handling Sheet.

Controls will not be given iron supplementation at enrolment but will receive the standard practice of nutritional counselling for blood donors. If someone not given iron supplements at enrolment is found to be anaemic, ID or IDA at a follow-up visit that individual will receive iron supplements.

All study participants will have nutritional counselling, dietary advice, and for those

receiving iron, the need for iron therapy to be used consistently 3 days a week.

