## 7.2 Parallel group trial

**Analysis cohort:** The intervention group is the group assigned oral iron supplementation at enrolment and the control group consists of those not assigned oral iron supplementation at enrolment.

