#### Primary analysis

The analysis for the primary outcome of haemoglobin levels at 4 months will be conducted using a linear model with haemoglobin levels at 4 months as the response variable. It is unlikely that there is a need to transform the response variable as haemoglobin levels are usually symmetrically distributed with tails that decay at rates consistent with the normal distribution. However, if informal univariate assessments of normality (e.g., qq-plots) indicate strong departures from these expectations, the Box-Cox transformation will be used to select a transformation. The set of explanatory variables will be group membership (i.e., received iron supplementation at enrolment or not), screening haemoglobin, sex, and age. A 1-sided t-test for the regression coefficient associated with group membership will be conducted with a significance level of 0.025 to test the inferiority hypothesis. This analysis will exclude individuals who did not receive iron supplementation at enrolment but received it during follow-up due to changes in ferritin or haemoglobin values. The frequency of this will be closely tracked and if more than 10% of participants in the group initially not receiving iron supplementation receive iron supplementation during follow-up, alternative analysis approaches will be considered and presented to the DSMB.

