## 7.2.2 Secondary outcomes

### Secondary outcomes related to efficacy

Several secondary outcomes relate to the efficacy of iron supplementation. The treatment of those not requiring iron supplementation at enrolment but requiring iron supplementation during follow-up will be the same as for the primary outcome. These secondary outcomes include:

- Change in haemoglobin over 4 months (g/dl).
- Ferritin levels at 4 months (µg/L).
- Diagnosis of ID or IDA at 4 months (Yes or No).
- Attempt to return for donation within 6 months (Yes or No).
- Successful donation within 6 months (Yes or No).

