### Secondary analyses of secondary outcomes related to safety and feasibility

To maximize the power to detect an association between group membership and safety outcomes, a composite of grade 3 and 4 AEs, SAEs, gastro-intestinal problems, malaria, and bacterial infections will be constructed and compared between the groups.

The frequency of this composite will be compared between groups using Fisher's exact test. Furthermore, logistic regression models will be fit with group membership, sex, and age as covariates and the odds ratio associated with group membership will be estimated along with a 95% confidence interval. These models will be parameterized so that an OR greater than 1 indicates that the intervention group has a higher incidence of negative outcomes. Components of the composite will also be investigated using a similar approach.

The questions about known side effects to iron supplementation ask: Has the participant experienced any of the following since the last visit (mark all that apply)?

- Unpleasant taste.
- Constipation.
- Dark tools.
- Nausea.
- Vomiting.
- Abdominal pain.
- Diarrhea.
- Other; specify.

The incidence of each of these outcomes over follow-up will be computed and logistic regression models will examine the impact of group membership, sex, and age on these outcomes. The odds ratio and a 95% confidence interval for the group membership variable will be used to summarize the association. Models which look at the incidence of any of these outcomes will also be examined and an odds ratio and 95% confidence interval will be used to summarize the relationship.

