#### 7.2.3 Sensitivity analyses

In the primary analysis, individuals are excluded if they did not receive iron supplementation at enrolment but received it during follow-up due to changes in ferritin or haemoglobin values. Sensitivity analyses will be conducted for the primary outcome by including those requiring iron supplementation during follow-up in the control group.

Since the treatment is not assigned at random there is a strong potential that confounders will introduce bias into the estimates of the treatment effects. As an attempt to remedy this, sensitivity analyses using inverse probability weighting will be conducted for the primary outcome and the secondary outcomes that relate to efficacy. If we use  $X_i$  to represent group membership for participant  $i$  and  $Z_i$  is a vector of predictors for this participant, the first step of the analysis is to estimate the stabilized inverse probability of "treatment" weights  $W_i$  for subject  $i$ ,  $W_i = P(X_i = x_i)/P(X_i = x_i|Z_i)$ . The predictors  $Z_i$  include age, sex, screening haemoglobin concentration, screening plasma ferritin concentration, socio-economic status, medical history, and diet. An estimate of  $P(X_i = x_i|Z_i)$  can be obtained by logistic regression

and  $P(X_i = x_i)$  can be estimated by the sample proportion. One then uses these weights in a regression model to adjust for participant characteristics that differ between the groups.

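### As written, the safety comparison counts events after a control starts iron as control events, which would dilute any excess risk from iron

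*SAP*

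**What the plan says.** **Comparator.** The acceptability objective (SAP 1.2, Primary Objectives; the Protocol's Primary Objectives agree) says: "This safety profile will be established by comparison to a similar group of participants who do not receive iron supplementation".

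**Group definition.** The analysis cohort statement that opens SAP 7.2, and so covers the whole trial analysis, says: "the control group consists of those not assigned oral iron supplementation at enrolment".

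**Later iron in controls.** Under SAP section 4, a control "found to be anaemic, ID or IDA at a follow-up visit that individual will receive iron supplements". The Protocol's Follow Up Assessments section likewise offers iron to these participants and says that this will be recorded in the study database.

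**Handling for efficacy.** SAP 7.2.1 says: "This analysis will exclude individuals who did not receive iron supplementation at enrolment but received it during follow-up". SAP 7.2.2 carries this over to the efficacy secondary outcomes, where the treatment of those "requiring iron supplementation during follow-up will be the same as for the primary outcome". The sensitivity analysis in SAP 7.2.3 is for the primary outcome and works by "including those requiring iron supplementation during follow-up in the control group".

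**Handling for safety.** In the safety part of SAP 7.2.2, for the composite and its components, "logistic regression models will be fit with group membership, sex, and age as covariates". For the solicited side effects: "The incidence of each of these outcomes over follow-up will be computed". Neither passage mentions controls who start iron.

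**The concern.** Controls who start iron are exposed to the treatment whose safety is in question. If they remain in the control group for safety, a gastrointestinal complaint that arises after they begin iron is tabulated as an event without iron. When iron raises the risk of such events, the control rate goes up and the group difference shrinks towards no difference. The safety profile of the supplement is one of the three strands of the primary objective. SAP 7.2.2 also says that the safety composite was built to gain power, and dilution works against that aim.

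Such crossover is foreseeable from the plan itself. The SAP sets a 10% trigger for reconsidering the primary analysis, counts later iron within the sample size allowance, and plans to estimate incident ID and IDA in the control group.

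**Working it through.** **1. What the text implies.** SAP 7.2 labels the groups by enrolment status. SAP 7.2.1 then removes control starters from the primary analysis, and SAP 7.2.2 does the same for efficacy secondary outcomes. For safety nothing removes them or stops counting at first iron, so the general label applies and their events fall in the control column. The window stated for solicited symptoms is the whole of follow-up; none is stated for the composite.

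**2. The plan's own figures.** There is no safety power, event rate or expected crossover rate to reproduce. The group size does reproduce: with margin 1.0, SD 1.89, true difference -0.3, one-sided alpha 0.025 and power 85%, n = 2 × (1.960 + 1.036)² × 1.89² / 0.7² = 130.9, so 131 per arm. Then 131/0.9 = 145.6, so 146 per arm and 292 in all.

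**3. Dilution.** Let x be the share of controls who start iron, p0 the risk without iron, p1 the risk with iron, and f the fraction of the excess risk that starters carry.

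- Control-group risk: p = p0 + x × f × (p1 − p0)
- OR = [p1/(1 − p1)] / [p/(1 − p)]

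The assumed risks are p0 = 0.10 and p1 = 0.30. With x = 0, OR = 0.4286/0.1111 = 3.86.

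| x | p, full risk (f = 1) | OR | p, half excess (f = 0.5) | OR |
|---|---|---|---|---|
| 10% | 0.12 | 3.14 | 0.11 | 3.47 |
| 20% | 0.14 | 2.63 | 0.12 | 3.14 |
| 30% | 0.16 | 2.25 | 0.13 | 2.87 |

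On the risk-difference scale the retained share is 1 − x × f: 90%, 80% and 70% at full risk; 95%, 90% and 85% at half.

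The full-risk column is the worst case under these assumptions. Iron starts only after a visit at 2, 4 or 6 months, leaving about 4, 2 or 0 of the 6 months exposed. Events before that are true control events.

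**4. Power.** This uses exact two-sided 5% Fisher power with 146 per group, again on assumed risks. The range runs from half excess to full risk.

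| Risks | x = 0 | x = 10% | x = 20% |
|---|---|---|---|
| 5% vs 15% | 78% | 73% to 66% | 66% to 53% |
| 10% vs 25% | 91% | 87% to 82% | 82% to 71% |
| 20% vs 35% | 79% | 74% to 69% | 69% to 57% |

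The loss is about 4 to 12 points at 10% crossover and 9 to 25 points at 20%.

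**5. A remedy to avoid.** Suppose control events were cut off at first iron but any-event logistic regression were kept. Take a constant control hazard with 10% risk over 6 months, and starters cut off at 4 months on average (an assumption). Their risk is then 1 − 0.9^(4/6) = 0.068. The control risk becomes 0.0968, 0.0936 or 0.0903 at 10%, 20% or 30% crossover, and the OR is 4.0, 4.2 or 4.3 against a true 3.9. Unequal windows bias the comparison the other way.

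**The case against.** **Analysis by enrolment group is legitimate.** It is a treatment-policy comparison, and later iron is part of what controls are offered. The sentence just before the comparator statement in SAP 1.2 describes the treated side by assignment at enrolment, so the comparator might be read as the same split. This stands as a reason to keep the by-assignment analysis. It does not make that analysis answer the question about people who do not receive iron.

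**The SAP never says that starters stay in for safety.** This is true. A reader might infer a deliberate rule, but the documents do not support that. The cohort label also heads the primary analysis, which then removes starters, so the label alone does not settle each analysis. What can be said is that, with no safety rule, the label is what applies.

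**Crossover is already watched.** SAP 7.2.1 tracks it and takes alternatives to the DSMB above 10%. AE records hold relationship to treatment and dates, and the closed report lists grade 3 and 4 events and SAEs. All of this helps interpretation, but the trigger is written for the primary analysis and none of it changes the group-level safety tables.

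**Counting to first iron has its own bias.** This also stands. Step 5 of the working shows the effect of unequal windows. The cut-off is set off by anaemia or ID, so it may be informative.

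**Conclusion.** The point holds as a minor one that is cheap to repair. Read together, the cohort definition and the safety models place post-iron events of control starters in the control group, at odds with the stated comparator. If iron raises event risk, the excess shrinks by 5% to 10% at 10% crossover and by 10% to 20% at 20% crossover. If iron does not raise risk, there is no dilution.

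Two stronger readings are tempting. One is to take 3.1, 2.6 and 2.3 as the odds ratios to expect. They rest on assumed event rates and give every starter the full iron risk. The 10% in the SAP is a trigger and, separately, an allowance shared with loss to follow-up; it is not a forecast of crossover. The other is to infer that the plan leans towards a finding of no harm. Nothing in the documents supports this, and the composite was designed to raise the power to detect a safety association.

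**What to change.** State in SAP 7.2.2 how controls who start iron are handled for safety, and present two analyses.

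1. Keep the comparison by enrolment group as planned.
2. Add a supportive exposure-based comparison in which control visits or person-time count as unexposed only up to first iron. Use a visit-level model (for example GEE logistic regression by visit) or a rate model (Poisson with a follow-up offset, which the SAP already uses for incident ID and IDA), not any-event logistic regression over unequal windows. The symptom questions ask about the time since the last visit, so events can be split at the visit where iron begins. Say also how iron-group follow-up after the planned 4 months of treatment is classed.
3. Report the number of control starters, and show their post-iron events in a separate row.
4. Confirm that the iron start date is captured. The Protocol says only that the supplementation is recorded.

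The cost is a paragraph of SAP text and one table, to be settled before database lock. The exposure-based analysis has slightly less control follow-up, and its cut-off may be informative, so it should be labelled supportive.

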### 7.2.1 Primary outcome

The **primary outcome** of the trial is haemoglobin level (g/dl) after 4 months.

#### Primary analysis

The analysis for the primary outcome of haemoglobin levels at 4 months will be conducted using a linear model with haemoglobin levels at 4 months as the response variable. It is unlikely that there is a need to transform the response variable as haemoglobin levels are usually symmetrically distributed with tails that decay at rates consistent with the normal distribution. However, if informal univariate assessments of normality (e.g., qq-plots) indicate strong departures from these expectations, the Box-Cox transformation will be used to select a transformation. The set of explanatory variables will be group membership (i.e., received iron supplementation at enrolment or not), screening haemoglobin, sex, and age. A 1-sided t-test for the regression coefficient associated with group membership will be conducted with a significance level of 0.025 to test the inferiority hypothesis. This analysis will exclude individuals who did not receive iron supplementation at enrolment but received it during follow-up due to changes in ferritin or haemoglobin values. The frequency of this will be closely tracked and if more than 10% of participants in the group initially not receiving iron supplementation receive iron supplementation during follow-up, alternative analysis approaches will be considered and presented to the DSMB.

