Analytical approaches to the analysis of data from the prevalence study will focus on univariate summaries but will also investigate risk factors for deferral, ID, and IDA. Exact confidence intervals for the probability of deferral, the probability of ID and the probability of IDA will be computed using the method first described by Clopper and Pearson. Logistic regression will be used to assess risk factors for these outcomes. For deferral, these risk factors will include age and sex but likely little else as the data we can obtain for these individuals is limited. For ID and IDA, the role of demographics will be investigated as well as other factors including socio-economic status, medical history, and diet. Final models for the impact of risk factors on deferral, ID, and IDA will include demographics and a selection of covariates found to have a statistically significant univariate association with each of these outcomes.

The analysis for the primary outcome of haemoglobin levels at 4 months will be conducted using a linear model with haemoglobin levels at 4 months as the response variable. It is unlikely that there is a need to transform the response variable as haemoglobin levels are usually symmetrically distributed with tails that decay at rates consistent with the normal distribution. However, if informal univariate assessments of normality (e.g., qq-plots) indicate strong departures from these expectations, the Box-Cox transformation will be used to select a transformation. The set of explanatory variables will be group membership (i.e.,

received iron supplementation or not), baseline haemoglobin, sex, and age. A 1-sided t-test for the regression coefficient associated with group membership will be conducted with a significance level of 0.025 to test the inferiority hypothesis. This analysis will exclude individuals who did not receive iron supplementation at baseline but received it during follow-up due to changes in ferritin or haemoglobin values. The frequency of this will be closely tracked and if more than 10% of participants in the group initially not receiving iron supplementation receive iron supplementation during follow-up, alternative analysis approaches will be considered and presented to the DSMB. At a minimum, sensitivity analyses which include those requiring iron supplementation during follow-up will be pursued. These analyses will include those requiring supplementation during follow-up in each of the 2 groups.

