Parallel groups' trial to assess the acceptability of iron supplementation: Using a non-inferiority design with a non-inferiority margin of 1 g/dL for haemoglobin levels at 4 months, a 1-sided alpha level of 0.025, at least 85% power and under the assumption that the true difference in the means is 0.3 requires 262 participants (131 per arm). This number has been increased to allow up to 10% loss to follow-up or iron supplementation for those initially not requiring supplements (such individuals will be excluded from the primary analysis: see Section 7.2.1 for further details), thus the sample size is 292. For efficiency, participants will be enrolled into both parts of the quantitative study.

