**Table 2: Precision of prevalence estimates for ID and IDA.**

Prevalence	Error Margin	95% Confidence Interval
0.2	0.046	0.15, 0.25
0.3	0.053	0.25, 0.35
0.4	0.056	0.34, 0.46
0.5	0.057	0.44, 0.56

**Parallel groups study:** The primary outcome for this portion of the study is haemoglobin levels at 4 months. Formally the null hypothesis for this outcome is inferiority of treatment of low haemoglobin with iron supplementation among those with

low haemoglobin at screening to no treatment among those without low haemoglobin at screening. The non-inferiority margin is fixed at a value of 1.0 g/dL. Based on recent work in West Africa, the DCC has access to haemoglobin measurements from 1548 individuals between the ages of 17 and 60 who weigh at least 50 kg. Among these individuals the standard deviation of haemoglobin was 1.89 g/dL (the mean was 13.4 g/dL). These individuals did not pass the strict screening criteria used by the NBSG, so this estimate might be slightly inflated and so our power calculations may be somewhat conservative. We specify an alpha level of 0.025 and require power of at least 85%. With these values we can determine the number of participants per arm if we assume a value for the true difference between the groups (the absolute value of this difference must be less than our margin and will generally be negative when the margin is positive to be consistent with the lack of superiority of iron supplementation). Table 3 presents the number of participants per arm under these assumptions for a selection of values for the true difference. We assume that the true difference is -0.3 g/dL and obtain a sample size of 131 participants per arm. If the true difference is larger than -0.3 g/dL (e.g., if there is no difference) then the power will exceed 85%. To allow for loss to follow-up and some participants requiring iron supplementation due to incident anaemia, ID or IDA the sample size has been increased to 292.

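### If the Box-Cox rule for 4-month haemoglobin is ever used, the 1 g/dL non-inferiority margin has no stated equivalent on the transformed scale

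*SAP*

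**What the plan says.** The primary outcome "of the trial is haemoglobin level (g/dl) after 4 months" (SAP 7.2.1). SAP 2.4 states: "The non-inferiority margin is fixed at a value of 1.0 g/dL". The clinical argument for that margin (SAP 1.2, Design; protocol, Design) is made by subtracting 1 g/dL from mean haemoglobin in each sex. The sample size is also worked out in g/dL: "We assume that the true difference is -0.3 g/dL and obtain a sample size of 131 participants per arm".

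SAP 7.2.1 regresses 4-month haemoglobin on group, screening haemoglobin, sex and age, and tests the group coefficient with a 1-sided t-test at 0.025. It says a transformation is unlikely to be needed, and then adds that "if informal univariate assessments of normality (e.g., qq-plots) indicate strong departures from these expectations, the Box-Cox transformation will be used to select a transformation". The protocol's Quantitative Data Analysis section carries the same rule ("the Box-Cox transformation will be used to select a transformation").

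Neither document gives a converted margin, a reference haemoglobin for a conversion, a back-transformation, or a statement that the g/dL test stays primary. The only provision for changing the margin is the review at 50% enrolment (SAP 1.2, Design; protocol, Design). That review is triggered by a low standard deviation of screening haemoglobin, not by a transformation.

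**The concern.** A non-inferiority test needs a null value on the scale of the coefficient being tested. In g/dL that value is -1, although SAP 7.2.1 leaves the reader to supply it from the margin. Box-Cox with lambda other than 1 is non-linear, so a fixed difference on the new scale corresponds to different g/dL differences at different haemoglobin levels. No single constant can stand for 1 g/dL for both men and women.

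If the rule fires, someone must choose lambda, the way the margin is converted, and the haemoglobin level at which it is anchored. The trigger is an informal look at the outcome itself, so these choices come after the outcome data are seen. SAP 2.3 says participants and investigators are not blinded. The primary conclusion could then depend on a choice that nobody wrote down in advance.

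**Working it through.** **Inputs.** Margin 1.0 g/dL, SD 1.89 g/dL, true difference -0.3 g/dL, 1-sided alpha 0.025 and power 85% (SAP 2.4). Haemoglobin means of 14.5 g/dL (men) and 13.0 g/dL (women) are from SAP 1.2, Design. They are the plan's illustrative screening means for non-deferred donors if half of donors are anaemic, not predicted control means at 4 months. Lambda values of 2, 0 (log) and -1 are assumptions, because the documents give none.

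**Step 1: the plan's own figure, in g/dL.** n per arm = 2 × SD² × (z₀.₉₇₅ + z₀.₈₅)² / (margin - 0.3)² = 2 × 1.89² × (1.960 + 1.036)² / 0.7² = 130.9, so 131. All five rows of Table 3 reproduce (65, 80, 101, 131, 179). Inflation: 262 / 0.90 = 291.1, so 292. The default design is sound on its own scale.

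**Step 2: what 1 g/dL becomes after Box-Cox.** With f(y) = (y^λ - 1)/λ, or log y at λ = 0, the transformed size of a 1 g/dL deficit is f(m) - f(m - 1):

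| λ | at m = 14.5 | at m = 13.0 |
|---|---|---|
| 2 | 14.0 | 12.5 |
| 1 | 1.0 | 1.0 |
| 0 (log) | 0.0715 | 0.0800 |
| -1 | 0.0051 | 0.0064 |

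Only λ = 1 gives one value for both.

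**Step 3: back to g/dL.** Set the transformed margin to equal 1.00 g/dL at 14.5, then solve f(13.0) - f(13.0 - d) = f(14.5) - f(13.5) for d:

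- λ = 2: (13.0 - d)² = 169 - 28 = 141, so 13.0 - d = 11.87 and d = 1.13.
- log: d = 13.0 × (1 - 13.5/14.5) = 0.90.
- λ = -1: 1/(13.0 - d) = 1/13.0 + 1/13.5 - 1/14.5 = 0.08203, so 13.0 - d = 12.19 and d = 0.81.

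The plan's margin argument puts the lowest tolerated mean for women at 12.0 g/dL, so that half pass the 12 g/dL copper sulphate test. At λ = 2 anchored on men, that mean is 11.87, and Φ((11.87 - 12)/1.89) is about 47%.

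**Step 4: effect of the anchor on the error rate.** This simulation used 131 per arm, normal data, SD 1.89, control mean 14.5, a true deficit of exactly 1 g/dL, an unadjusted t-test and 4000 runs. The nominal rate of declaring non-inferiority is 0.025.

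| Scale | Anchor 13.0 | Anchor 13.4 | Anchor 14.5 |
|---|---|---|---|
| g/dL (no anchor needed) | 0.024 | 0.024 | 0.024 |
| log | 0.066 | 0.045 | 0.023 |
| λ = 2 | 0.008 | 0.012 | 0.022 |

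The 14.5 anchor does well because the simulated control mean is 14.5. The table shows that an unstated choice moves the error rate. It does not predict this trial's error rate.

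**Step 5: would mixing sexes and arms trigger the rule by itself?** I simulated 262 outcomes with sexes 1.5 g/dL apart (14.5 - 13.0), arms 0.3 or 1.0 g/dL apart, 50% or 70% men (assumed) and within-cell SD 1.89. Skewness lay between about -0.04 and 0, and excess kurtosis between about -0.04 and -0.02. A Shapiro-Wilk test at 5% rejected in roughly 4 to 6% of samples, which is close to its nominal rate. The mixture is close to normal.

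**The case against.** The strongest reply is that the plan expects no transformation and says so in both documents. The rule needs strong departures, and everything in the default path (outcome, margin, sample size, test) is consistently in g/dL. This stands: the point concerns a contingency. A reader might infer that the primary hypothesis has already lost its margin, or that the sample size is wrong. The documents support neither.

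A reader might also infer that pooling two sexes and two arms would make the outcome look non-normal and set the rule off falsely. Step 5 shows no such effect at the plan's SD. It appears only at a much smaller assumed SD: at 0.8, up to about 40% of samples were rejected. Residuals are still the right thing to inspect, because the t-test relies on them, but no false trigger should be claimed.

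A third tempting reading puts the number 1.0 directly on a log axis, which would tolerate an absurd deficit. Nothing in the plan says this would be done. A workable conversion does exist. With the form of Box-Cox scaled by the geometric mean (assumed 13.3), a margin of 1 means 1.05 and 0.94 g/dL (men and women) on the log scale, 0.95 and 1.07 at λ = 2, and 1.10 and 0.89 at λ = -1. That makes the ambiguity about 5 to 11%. The SAP does not specify this form, so the gap remains, but its size depends on the conversion chosen.

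Finally, SAP 1.1 allows updates before database lock. That makes the gap easy to close. It does not close it.

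**Conclusion.** The point holds as a conditional one. If the Box-Cox rule fires with λ other than 1, the primary 1-sided test has no defined null value, and the scale and margin conversion would be settled after outcomes are seen. In the illustration, a margin of 1.00 g/dL at 14.5 g/dL is worth 0.81 to 1.13 g/dL at 13.0 g/dL. This range rests on assumed lambdas, on the plan's illustrative screening means, and on anchoring at the male value. If λ is close to 1, the effect is negligible. The plan's default analysis and its 131 per arm stand. The change should still be made, because the rule sits inside the primary analysis and, if used, could change the conclusion.

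**What to change.** Change SAP 7.2.1 and the matching paragraph of the protocol's Quantitative Data Analysis so that:

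- the primary analysis always uses 4-month haemoglobin in g/dL, with the null value of -1 g/dL written out;
- normality is judged on the residuals of the fitted model, not on the raw outcome;
- if residuals depart strongly from normality, the same linear model is kept, with a heteroscedasticity-robust or bootstrap 95% confidence interval for the group coefficient (one of the two named in advance), and its lower bound is compared with -1 g/dL;
- any Box-Cox analysis is reported as a sensitivity analysis.

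A second valid repair is to keep the transformation and pre-specify the back-transformation and the covariate values at which 1 g/dL is assessed. It is more elaborate and harder to explain.

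The cost is a few sentences in each of two documents before database lock. With about 130 per arm, little is lost by staying in g/dL. The one downside is a possible small loss of efficiency if the outcome turns out strongly skewed, since robust or bootstrap intervals do not recover it.
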